### **Safety Index**

1. Adverse events;
2. Vital signs;
3. Physical examination;
4. Laboratory tests(Including complete blood count, routine urine, blood biochemical examination, prolactin);
5. ECG: 12 leads cardiogram;
6. Scale evaluation(SAFTEE).

## Flow chart of experiment

## Dealing with Adverse Event

In the study, doctors will monitor the side effects of drugs. If subjects have side effects, the doctor will treat them accordingly. If the subjects could not tolerate side effects, they will be stopped to take research drugs and withdraw from the study.

**A Randomized, Parallel-group, Placebo-controlled, Double-blind Clinical Trial to
Evaluate the Efficacy and Safety of Ethosuximide in Chinese Patients with
Treatment-Resistant Depression**

Statistical Analysis Plan

(Registration Number: 2019-716)

Version Number: 2.0 Date:12 April 2019 (Protocol version Number: 3.0)

1. Study purpose

The aim of this study is to evaluate the clinical efficacy and safety of ethosuximide in patients with treatment-resistant depression.

2. Study design

2.1 Study Overview

This is a randomized, parallel-group, placebo-controlled and double-blind study conducted by a single center. In the study, ethosuximide or placebo will be given for 2 weeks in experimental group or control group and escitalopram will be given for the next 4 weeks in each group.

usage and dosage:

Ethosuximide, 2 times/day, take it orally after breakfast/dinner; take 500mg in the morning and 500mg in the evening on day1, 500mg in the morning and 750mg in the evening on day2, 750mg in the morning and 750mg in the evening on day3, 750mg in the morning and 1000mg in the evening on day4, 1000mg in the morning and 1000mg in the evening on day5, maintain this dose until the end of treatment for 2 weeks.

The usage and dosage of placebo are the same as above.

Escitalopram, 1 time/day, 20mg/day, take it orally after breakfast, take it for 4 weeks without interruption.

2.2 Sample Size

We will recruit 40 subjects, 20 in the experimental group and 20 in the control group.

3. Analytical parameters

3.1 Validity Index

3.1.1 Main efficacy measures

Changes of Montgomery–Asberg Depression Rating Scale (MADRS) score at therapeutic visit point compare with baseline.

3.1.2 Secondary efficacy measures

Changes of Quick Inventory of Depressive Symptomatology – Self Report (QIDS-SR) score at therapeutic visit point compare with baseline.

Changes of Hamilton Anxiety Rating Scale (HAMA) score at therapeutic visit point compare with baseline.

Changes of individual score of MADRS at therapeutic visit point compare with baseline.

Changes of Young Mania Rating Scale (YMRS) score at therapeutic visit point compare with baseline.

Efficacy after 2 and 4 weeks of treatment.(Efficacy means that the score of MADRS decreasing by more than or equal to 50% compares with its baseline score)

Remission rate after 2 and 4 weeks of treatment.(Remission means that the total score of MADRS is less than 10.)

3.2 Safety Index

Adverse events, Vital signs, Physical examination, Laboratory tests(Including complete blood count, routine urine, blood biochemical examination, prolactin), ECG: 12 leads cardiogram, Scale evaluation.

4. Patient population analysis

4.1 Efficacy Set

Efficacy Set contains a set of subjects that meet all the following requirements.

- 1) All patients who are received study drug.
- 2) Patients who have scale scoring data at least at one time point after drug administration.

The Efficacy Set will be used for analysis of the efficacy of drugs.

4.2 Safety Set

Safety Set contains a set of subjects that meet all the following requirements.

- 1) All patients who are received study drug.
- 2) All patients who have safety data.

The Safety Set will be used for analysis of demographic and baseline characteristics and the safety of drugs.

5. Statistical method

5.1 General Principles

The analysis will be performed after data collection is completed. Statisticians and relevant researchers of the study group will use the latest version of SPSS statistics for data analysis, and all data analysts are blinded to treatment allocation.

The research data are mainly analysed on the basis of intention-to-treat (ITT) principle. All randomized participants are analysed according to the intervention to which they are randomized initially in the ITT analysis. The per-protocol (PP) analysis is another analysis method. In the per-protocol (PP) analysis, participants who do not receive treatment or do not provide any follow-up data should be excluded and grouped to analyse according to the intervention they actually received.

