#### **Withdrawal criteria**

Subjects withdrawing from the study: subjects who quit voluntarily and who need to withdraw after medical assessment of researchers.

1. Subjects who break off informed consents at any time;
2. Subjects who are lost to follow-up;
3. Severe adverse events, or intolerable adverse events happen, and are identified by the researchers that subjects need to quit;
4. Subjects who violate the protocol severely that affect the assessment of safety and efficacy of the research definitely;
5. Subjects who get psychiatric symptoms, mania, suicidal or self-injurious behaviors during the study;
6. Subjects who are pregnant during the study;
7. Subjects need to withdraw from the study in other situations after assessment of researchers.

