#### **Prohibited drug and prohibited treatment**

Prohibited drug:

1. Antipsychotics, antidepressants, mood stabilizers, antianxiety drugs, central stimulants and any other psychotropic drugs (except those permitted for combination);
2. Chinese medicines with antidepressant effects specified in the instructions.

Prohibited treatment:

1. Antipsychotics, antidepressants, mood stabilizers, antianxiety drugs, central stimulants and any other psychotropic drugs (except those permitted for combination).
2. Chinese medicines with antidepressant effects specified in the instructions.

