#### **Combined medication and treatment**

1. In the study, zolpidem, zopiclone, Eszopiclone and zaleplone are allowed to be combined for the treatment of insomnia and taken before retiring. The dosage should not exceed the upper limit specified in the instructions, and the cumulative use time of the study period after randomization should not exceed one week.
2. Drugs for the treatment of original somatic diseases are permitted to take. But the types and doses of drugs should be kept as constant as possible in the study.

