### **Methods of drug administration**

Subjects with treatment-resistant depression who meet the inclusion criteria and do not meet the exclusion criteria are randomly assigned to the following two study groups:

Group 1: A (2 weeks) + C (4 weeks)

Group 2: B (2 weeks) + C (4 weeks)

A: Ethosuximide (capsule, 250mg/capsule)

B: Placebo (capsule, 250mg/capsule)

C: Escitalopram (tablet, 10mg/pill)

usage and dosage:

Drug A, 2 times/day, take it orally after breakfast/dinner; take 500mg in the morning and 500mg in the evening on day1, 500mg in the morning and 750mg in the evening on day2, 750mg in the morning and 750mg in the evening on day3, 750mg in the morning and 1000mg in the evening on day4, 1000mg in the morning and 1000mg in the evening on day5, maintain this dose until the end of treatment for 2 weeks.

The usage and dosage of Drug B are the same as above.

Drug C, 1 time/day, 20mg/day, take it orally after breakfast, take it for 4 weeks without interruption.

The time of the first administration should be after the next day's breakfast randomly. If the patient had taken escitalopram or was allergic to escitalopram in the past, the researchers would choose another appropriate antidepressant according to the patient's condition. Medication cycle: The study drugs will be taken for 6 weeks.

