5.2 Handling of Missing data

Unless otherwise specified, missing values will not be imputed.

[figure not shown]

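### The SAP's per-protocol set is essentially the Efficacy Set, so agreement with ITT cannot show robustness to breaches of the psychotropic ban or hypnotic cap by patients who stay in the study

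*SAP*

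**What the plan says.** SAP section 5.1 makes ITT the main analysis, with everyone randomised analysed in the arm assigned. It then names per-protocol as a second method. In that analysis "participants who do not receive treatment or do not provide any follow-up data should be excluded", and patients are grouped by the treatment they actually received.

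SAP section 4.1 defines the Efficacy Set by two conditions: the patient received study drug, and belongs to the "Patients who have scale scoring data at least at one time point after drug administration". Section 5.2 adds: "Unless otherwise specified, missing values will not be imputed".

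The protocol sets two rules on other medication:

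- **Prohibited drug and prohibited treatment** bans antipsychotics, antidepressants, mood stabilisers, anxiolytics, stimulants and "any other psychotropic drugs (except those permitted for combination".
- **Combined medication and treatment** permits four named hypnotics for insomnia, but "the cumulative use time of the study period after randomization should not exceed one week".

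Two items under Withdrawal criteria could apply to a breach. Item 4 reads "Subjects who violate the protocol severely that affect the assessment of safety and efficacy of the research definitely" and item 7 reads "Subjects need to withdraw from the study in other situations after assessment of researchers". Neither mentions the ban or the cap.

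**The concern.** A per-protocol analysis is normally read as asking whether the result holds among patients who followed the protocol. Here nothing in the definition refers to following it. Other psychotropics and regular hypnotics can both move depression ratings; MADRS itself is the main efficacy measure and is compared between arms for two weeks without any other antidepressant. These are the breaches such an analysis would be expected to set aside.

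If the set keeps those patients, it will agree with ITT almost automatically. A reader could then take the agreement as evidence that breaches did not matter, although no patient was left out for a breach.

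**Working it through.** The SAP gives no figure for the per-protocol set, so there is none to reproduce. The check is mainly a comparison of definitions, followed by two small calculations.

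**Inputs.** Per-protocol rule and ITT rule: SAP 5.1. Efficacy Set: SAP 4.1. No imputation: SAP 5.2. Ban and cap: protocol medication sections. Rating days: protocol visit sections. Sample size, 20 per arm: SAP 2.2.

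**Step 1: per-protocol set against Efficacy Set.** Let T = received study drug, F = has any follow-up data, S = has a post-dose scale score, V = breached the ban or cap but stayed in the study. A patient with S also has F.

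- Per-protocol set = T and F.
- Efficacy Set = T and S.
- In the Efficacy Set but not per-protocol: none, because S implies F.
- In the per-protocol set but not the Efficacy Set: patients dosed, with some follow-up data but no post-dose score. MADRS is scheduled at every post-baseline visit, so this group should be close to empty. Its members would have no efficacy score to analyse in any case.
- V appears in neither definition.

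**Step 2: per-protocol set against ITT.** With no imputation, a randomised patient who has no follow-up score has no change from baseline under ITT either. That leaves two ways to differ: patients rated but never dosed, whom per-protocol drops, and patients given the other arm's drug, whom it regroups. Neither concerns other medication.

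**Step 3: effect of a breach on membership.** If k of the 40 patients breach the ban or cap and stay in with ratings, the SAP's set removes 0 of them for every k. With all 40 otherwise eligible, a set that excluded them would hold 40 − k: 38 for k = 2, 36 for k = 4, 32 for k = 8. These k are illustrations; the documents give no rate.

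**Step 4: when the cap could be passed.** A patient using a hypnotic every night from Day 1 uses the allowed week on Days 1 to 7 and passes the cap on Day 8. Post-baseline ratings in the ethosuximide-versus-placebo phase fall on Days 2, 3, 4, 6, 10 and 14. Two of the six (Days 10 and 14) come after that point, and Day 14 carries the 2-week response and remission measures. The other three ratings (Days 22, 29 and 42) fall in the escitalopram phase. This is the earliest case; later or intermittent use would pass the cap later or not at all.

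**Step 5: price of a real per-protocol set.** For a difference in means with n per arm and the same standard deviation, the standard error is proportional to √(2/n), so its ratio to the full set is √(20/n).

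| Excluded per arm (assumed) | n per arm | Ratio | Increase |
|---|---|---|---|
| 1 | 19 | √(20/19) = 1.026 | about 3% |
| 4 | 16 | √(20/16) = 1.118 | about 12% |

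**The case against.** The strongest case against has four parts.

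- **Severe breaches already have a rule.** Withdrawal item 4 can reasonably be read to cover a patient who takes a prohibited antidepressant. Once withdrawn, with later scores missing and not imputed, that patient would tend to fall out of the repeated-measures ANOVA in SAP 5.4. This stands, and it narrows the point to patients who stay in, probably with milder breaches. It does not rescue the set: withdrawal leaves data already collected in both sets, and where a patient does drop out of the ANOVA, this happens under ITT and per-protocol alike.
- **The setting limits breaches.** Patients enter as inpatients and combined medication is recorded at every visit. That makes unnoticed breaches less likely, although the documents do not promise a six-week stay. It bears on how often breaches occur, not on what the set can detect.
- **The two exclusions are not called exhaustive.** True, but no other section of either document adds one.
- **Nothing says agreement will be presented as robustness, and this is a preliminary 40-patient trial.** Also true. It limits the consequence and leaves the definition as it is.

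A reader might also infer that the set is undermined by someone who takes only the Day 1 capsules and is rated once on Day 2. Such a patient does meet the definition. However, the ANOVA in SAP 5.4 runs over all rating times and in its ordinary form needs each of them, so with no imputation this patient would normally not enter it under any set. The example shows membership, not influence, and the point does not rest on it.

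**Conclusion.** The point holds for patients who breach the ban or cap and remain in the study. For them the per-protocol analysis repeats the Efficacy Set apart from grouping by treatment received, and excludes 0 patients whatever the number of breaches. Its agreement with ITT is uninformative about those breaches.

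A reader might go further and infer that the main result is biased. The documents do not support that. ITT is the main analysis and is not invalidated by a weak supportive set, and with no breach rate and no effect of a breach stated, no size of bias can be derived.

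The conclusion rests on taking the two exclusions in SAP 5.1 as the complete list, because neither document gives another. The change is worth making before unblinding: the stated rule fails at its purpose and the correction is cheap.

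**What to change.** **SAP 5.1.** Define the per-protocol set as Efficacy Set patients who, through Day 14, took no drug on the protocol's prohibited list and used permitted hypnotics on no more than 7 cumulative days. Fix membership on blinded data before unblinding. Use this one set for a supportive repeated-measures analysis of the Day 2 to Day 14 ratings, and keep ITT as the main analysis. Restricting it to the ethosuximide-versus-placebo phase gives one population for one model.

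If a later-phase per-protocol analysis is wanted, apply the same rule through Day 42 as a separate set with its own model. Trial escitalopram must not count as a breach there, nor its substitute where, under Methods of drug administration, "the researchers would choose another appropriate antidepressant".

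**Protocol.** State that exceeding the hypnotic cap is recorded as a deviation and that scheduled ratings continue where the patient consents. This removes case-by-case judgement about whether such a patient keeps being rated, and protects the ITT data.

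**Cost.** One redefined set, a short protocol addition and no new data collection, assuming the combined-medication records allow hypnotic days to be counted. The new set is smaller and selected after randomisation, so it can only support ITT. Its standard error would be about 3% to 12% larger under the assumed 1 to 4 exclusions per arm.

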5.2 Handling of Missing data

Unless otherwise specified, missing values will not be imputed.

[figure not shown]
5.3 Subjects Characteristics

5.3.1 Subjects Disposition

Subject enrollment and disposition will be summarized.

The number and percentage of completed and withdrawn subjects will be summarized.

The details of incomplete study subjects will be listed.

5.3.2 Demographic and Baseline Characteristic

Baseline characteristics

	Ethosuximide + Escitalopram(n)	Placebo + Escitalopram(n)
Age, years		
Sex, F (% n/N)		
BMI, kg/m ²		
Years of education		
Vital signs		
Blood pressure (sitting position)		
Heart rate		
Respiratory rate		
Body temperature		
Physical examination of clinical significance		

Abnormal values of laboratory examination

Abnormal results of 12-Lead Electrocardiograms

Age at onset of first major depressive episode (years)

Lifetime number of major depressive episodes

Duration of current episode (weeks)

Montgomery–Åsberg Depression Rating Scale (MADRS) score

Young Mania Rating Scale (YMRS) score

Hamilton Anxiety Rating Scale (HAMA) score

Quick Inventory of Depressive Symptomatology – Self Report (QIDS-SR) score

5.4 Clinical Efficacy of Drug Treatment Analysis

The efficacy of drugs will be judged by analyzing the changes from baseline to treatment point in each scale score. Two-way Repeated Measures Anova will be used to compare the efficacy between experimental and control group; intervention measures will be defined as inter-group variables, and time points of scale evaluation as inner-group variables. First, the scale scores of each participant at baseline and each treatment point be listed (Table 2), and the average value of each group will be calculated. Then, values of sum of squares of deviation from mean, degree of freedom and mean square will be calculated. After calculating F values of inter-group factors or inner-group variables, the corresponding P values by querying F value threshold table and statistical inferences will be determined. It should be noted that the degree of freedom of inner-group variables needs to be corrected in the statistical test.

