rats), 300 mg/kg ethosuximide was given daily through drinking water for 17 consecutive days at the age of 5 months with obvious epileptic seizures, which resulted in significant antidepressant effect (the immobility time of forced swimming was significantly reduced).

In conclusion, ethosuximide can inhibit the T-VSCCs on the lateral habenular nucleus neurons and then inhibit the cluster discharges of neurons, resulting in a rapid antidepressant effect. The purpose of this study was to explore the antidepressant efficacy of ethosuximide tablets in patients with refractory depressive disorders, to preliminarily evaluate the clinical efficacy and safety, and to explore the possible mechanism of its antidepressant effect.

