### **Treatment Period (Day 2) - Visit 2**

Visit will be conducted on day2 after randomization(24 hours after taking medicine).

Contents of visit:

1. Scale score: MADRS、 QIDS-SR、 HAMA、 YMRS;
2. Vital signs: including blood pressure (sitting position), heart rate, respiratory rate, body temperature and weight;
3. Records of adverse event;
4. Records of combined medication;
5. Drugs recovery and dispensing.

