## **Observation measures**

### **Validity Index**

#### **Main efficacy measures**

Changes of MADRS score at therapeutic visit point compare with baseline.

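### The primary MADRS measure names no visit, and the only between-arm F in SAP 5.4 averages six ethosuximide-phase visits with three from the escitalopram phase

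*SAP*

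**What the plan says.** The Protocol (Main efficacy measures) defines the primary measure as "Changes of MADRS score at therapeutic visit point compare with baseline". SAP 3.1.1 has the same content: "Depression Rating Scale (MADRS) score at therapeutic visit point compare with baseline". Neither names a day or week. Only the secondary response and remission measures carry times, 2 and 4 weeks (SAP 3.1.2).

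SAP 5.4 contains the efficacy analysis: "Two-way Repeated Measures Anova will be used to compare the efficacy between experimental and control group", with arm as the between-subject factor and time of assessment as the within-subject factor. On testing it says: "After calculating F values of inter-group factors or inner-group variables, the corresponding P values by querying F value threshold table". It does not mention group-by-time, per-visit contrasts or a significance level.

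On the outcome, SAP 5.4 opens with "The efficacy of drugs will be judged by analyzing the changes from baseline to treatment point in each scale score". Its computing steps, however, start from a listing of each participant's scores at baseline and at every later assessment.

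On design, ethosuximide or placebo is titrated over five days; the instruction is then to "maintain this dose until the end of treatment for 2 weeks". Both arms next take escitalopram for four weeks, or another antidepressant where the Protocol allows a substitute. The stated rationale is that the drug will "inhibit the cluster discharges of neurons, resulting in a rapid antidepressant effect" (Protocol, Introduction).

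**The concern.** The aim in SAP section 1 is the efficacy of ethosuximide, which is given only in weeks 1 and 2. If the primary test averages over all six weeks, a third of its weight falls on visits when neither arm takes ethosuximide. It then compares ethosuximide-then-escitalopram with placebo-then-escitalopram. That is a legitimate question, but not the stated one.

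Two further gaps add to this. Standard software will print a group-by-time F beside the group F, and the SAP does not say what to do with it. The SAP also does not settle whether baseline is subtracted out or entered as a time level, and that choice changes the meaning of both tests. A reader of the results could not tell which number was meant to answer the primary question. SAP section 6 allows the plan to change as the study proceeds.

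**Working it through.** **Inputs from the documents**

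- MADRS is scored at baseline (Day 1) and on Days 2, 3, 4, 6, 10, 14, 22±1, 29±1 and 42±1 (Protocol visit sections).
- The first treatment visit follows dosing: "Visit will be conducted on day2 after randomization(24 hours after taking medicine".
- Ethosuximide/placebo lasts two weeks, so six post-baseline visits fall in that phase and three after it. If the first dose is a day after randomisation, Day 14 is still inside the phase and Day 22 (earliest Day 21) still outside.
- There are 20 subjects per arm (Protocol, Number of subjects; SAP 2.2).

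The documents give no significance level, power, effect size, SD or correlation, so there is no planned figure to reproduce. Everything below that depends on such values is an assumption.

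**Step 1. What the group F estimates.** With balanced data it equals the square of a two-sample t on each subject's mean over the K time levels. Its target is (sum of arm differences over the levels)/K. For an effect constant on drug and zero afterwards:

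- nine change scores: 6/9 = 0.67 of the effect;
- ten raw scores with baseline as a level: 6/10 = 0.60.

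**Step 2. An assumed 8-point Day 14 effect under five time courses.** "Builds" means linear from Day 1, so the fractions on Days 2 to 14 are (day − 1)/13 and sum to (1+2+3+5+9+13)/13 = 2.54. "Fades" means linear to zero at Day 42, so Days 22, 29 and 42 add (20+13+0)/28 = 1.18. The target is 8 × sum/K; for the last column, 8 × (sum over Days 2 to 14)/6.

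| Time course | Sum of nine fractions | Nine changes (÷9) | Ten raw scores (÷10) | Mean of Days 2–14 |
|---|---|---|---|---|
| Builds, gone by Day 22 | 2.54 | 2.3 | 2.0 | 3.4 |
| Builds, fades to Day 42 | 3.72 | 3.3 | 3.0 | 3.4 |
| Builds, persists | 5.54 | 4.9 | 4.4 | 3.4 |
| Immediate, gone by Day 22 | 6 | 5.3 | 4.8 | 8.0 |
| Immediate, persists | 9 | 8.0 | 7.2 | 8.0 |

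**Step 3. What this does to power.** Power is from the noncentral t with 38 df and noncentrality d × m/√v × √(20/2), where m is the mean effect fraction and v = (1 + (K − 1)ρ)/K. Assumptions: two-sided 0.05, standardised effect d = 0.8, equal SDs, one common correlation ρ, no dropout, no baseline adjustment. A single Day 14 comparison (m = 1, v = 1) has 69%.

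| Pattern | Contrast | ρ = 0.3 | 0.5 | 0.7 | 0.9 |
|---|---|---|---|---|---|
| Constant on drug, none after | Nine-visit group F | 76% | 60% | 48% | 41% |
| | Ten-level group F | 68% | 51% | 41% | 34% |
| | Mean of Days 2–14 | 97% | 90% | 81% | 73% |
| Builds (0.1, 0.2, 0.4, 0.6, 0.8, 1.0), none after | Nine-visit group F | 28% | 21% | 17% | 14% |
| | Mean of Days 2–14 | 51% | 39% | 31% | 27% |
| Constant through Day 42 | Nine-visit group F | 98% | 91% | 82% | 73% |

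The loss depends on the time course. In the last pattern there is none, and at ρ = 0.3 averaging beats Day 14 even in the first (76% against 69%).

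**Step 4. Group F and group-by-time F.** On change scores, an immediate constant effect is the same at all nine visits, so it produces no interaction. With baseline as a tenth level, the same effect is a step from zero and does produce one. Simulation with an 8-point effect (20 per arm, SD 4.5 rising to 9, correlation 0.4 to 0.6, all assumed) shows the consequence for an immediate, persistent effect:

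- change scores: group-by-time power is 3–5%, and the two tests differ in significance in 95–97% of trials;
- ten raw scores: group-by-time power is 68–100% and the tests differ in 1–32%, across two sets of covariance settings.

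For an effect that builds and is gone by Day 22, the tests differ in 42–67% of trials on change scores and in 64–75% on raw scores.

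With no drug effect, counting either test as success gives 1 − 0.95² = 9.75% if the two are independent, and 8–10% in simulation, instead of 5%.

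**The case against.** SAP 5.4 does say that the ANOVA is there to compare the arms, and it names the between-group F. A fair reader would take that F as the intended primary test. It is valid for the randomised sequences, and it performs well when onset is immediate or the effect lasts. The Introduction's rapid-onset rationale makes a slow build less likely. Analysts are blinded (SAP 5.1), the trial is described as preliminary, and no power claim is made. Table 2 of the SAP and the protocol flow chart are not legible in the text reviewed, so they could limit the time points. Most of this stands. It lowers the severity, but it does not supply a visit, a phase or a role for the interaction.

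A reader might infer more than the documents support:

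- **That the plan has no between-arm test, or that the time F could count as success.** The stated purpose of comparing groups points to the group F; the wording is loose, not empty.
- **That the two F tests give opposite primary answers in nearly every trial.** The 95–97% figure belongs to one time course on change scores. Moreover, a significant group F with a non-significant interaction is what a constant effect should give: the tests ask different questions.
- **That the primary analysis carries a nine-visit multiplicity problem.** SAP 5.4 plans one ANOVA, not nine visit-wise tests.
- **That Day 14 is the only defensible visit.** The secondary measures name 2 and 4 weeks, and the rationale favours early effects. If the effect is 8 points to Day 6 and 4 by Day 14, Day 14 ANCOVA has about 31–52% power under the simulation assumptions, against 98–100% for the Days 2–14 mean.

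**Conclusion.** The concern holds in this form: no primary visit is named, the time points are not restricted, and the one between-arm F that SAP 5.4 names mixes the drug phase with the escitalopram phase. The 6 + 3 visit split and the factors 0.67 and 0.60 follow from the schedule, given an effect constant on drug and absent afterwards. The point differences and powers rest on assumed effects, SDs, correlations and time courses, and range from a large loss (8 points averaged to 2.3) to none. The uncertainty over change scores or ten raw scores is a separate gap, which alters the meaning of both F tests. The false-positive rate of about 8–10% applies only if either F were allowed to count, which the SAP neither proposes nor excludes. For a preliminary trial of 40 with no stated power, this is a should-fix point.

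**What to change.** Before unblinding, amend the Protocol (Main efficacy measures) and SAP 3.1.1 and 5.4:

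1. Name one primary between-arm contrast inside the ethosuximide/placebo phase, tested two-sided at 0.05: either baseline-adjusted MADRS change at Day 14, or baseline-adjusted mean change over Days 2 to 14. The mean is more robust if onset is rapid, as the Introduction expects; four of its six visits fall by Day 6. Day 14 is better if the effect builds.
2. Estimate it by ANCOVA with baseline MADRS, or by a mixed model with baseline, group, visit and group-by-visit. State the covariance structure and degrees-of-freedom method in advance and keep them feasible: an unstructured matrix has 9 × 10/2 = 45 parameters over nine visits, or 6 × 7/2 = 21 over six, with 40 subjects. The mixed model uses all observed visits without imputation, in line with SAP 5.2. If ANCOVA on the mean is chosen, say how the mean is formed when a visit is missing.
3. State that the outcome is change from baseline, with baseline as a covariate and not as a time level.
4. Make Days 22, 29 and 42 secondary (durability), make the nine-visit group F and the group-by-time F supportive, and say that the time main effect is not evidence of efficacy.

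The cost is a short protocol amendment and SAP wording, with no new visits or data. Durability to Day 42 becomes secondary, and some power is lost if the chosen contrast does not match the true time course.
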